#### **6.8.1.6 Follow-up of Adverse Events and Serious Adverse Events**

All AEs and SAEs assessed as not related to study drug or procedure, including clinically significant laboratory tests, or physical examination findings, must be followed until the event resolves, the condition stabilizes, the event is otherwise explained, or the final study visit occurs, whichever comes first.

AEs and SAEs assessed as related to study drug or procedure will be followed for as long as necessary to adequately evaluate the patient’s safety, or until the event stabilizes, or the patient is lost to follow up. If resolved, a resolution date should be provided.

The investigator is responsible for ensuring that follow-up includes any supplemental investigations indicated to elucidate the nature and/or causality of the event. This may include additional clinical laboratory testing or investigations, examinations, histopathological examinations, or consultation with other health care professionals as is practical, according to the Sponsor’s requests.

Defibrotide (JZP-381)  
Clinical Trial Protocol: 15-007 Version 4.0

Jazz Pharmaceuticals, Inc.  
20 August 2018

---

The Investigator should provide follow-up SAE information for any updates to information previously provided to the Sponsor.

#### 6.8.1.7 **Pregnancy**

Pregnancy of a patient or a male patient's partner must be reported within 24 hours of first knowledge of the event by study site personnel.

If a patient or a male patient's partner becomes pregnant any time after the first dose of study drug until 30 days after the last dose of study drug, the pregnancy form should be used to report the pregnancy to the Sponsor or its designee, and study medication must be stopped for any pregnant patient. The pregnancy of a patient or a male patient's partner must be followed until the outcome of the pregnancy is known, and in the case of a live birth, for 6 months following the birth of the child. The infant follow-up form should be used to report information regarding the status of the infant.

#### 6.8.1.8 **Regulatory Reporting**

The Sponsor or its designee is responsible for reporting to the relevant regulatory authorities, central ethics committees (CECs), and participating investigators, and will report in accordance with ICH guidelines, the US Code of Federal Regulations (CFR), the European Union (EU) Clinical Trial Directive, and local regulatory requirements.

The reference safety information to determine expectedness of SAEs is specified in the Investigator's Brochure for defibrotide.

Suspected serious unexpected adverse reactions (SUSARs) that are fatal or life-threatening will be reported to the relevant regulatory authorities, CECs, and participating investigators no later than 7 days after knowledge of such a case, and relevant follow-up information provided within an additional 8 days.

All other SUSARs (i.e., non-fatal or life-threatening) will be reported to the relevant regulatory authorities, CECs, and all participating investigators no later than 15 days after first knowledge of the event.

Once a year throughout the clinical study, a report listing of all SUSARs (and SAEs if required by local regulation) that have occurred during this period and a report of the patient's safety will be submitted to the applicable authorities, and as otherwise required by local laws.

Reporting of SAEs by the investigator to his/her local IEC will be done in accordance with the standard operating procedures and policies of the IEC. Adequate documentation must be maintained showing that the IEC was properly notified.

Defibrotide (JZP-381)  
Clinical Trial Protocol: 15-007 Version 4.0

Jazz Pharmaceuticals, Inc.  
20 August 2018

## 6.8.2 Clinical Laboratory Tests

Clinical laboratory tests will be performed at local laboratories. It is anticipated that patients will undergo laboratory testing both as an inpatient and an outpatient. The investigator will provide to the Sponsor or its designee the current licensure and laboratory reference ranges for all laboratories used during the study.

### 6.8.2.1 Laboratory Parameters

Clinical laboratory tests will include serum chemistry, hematology, and coagulation (Table 7). Collection frequency is outlined in the Schedule of Procedures and Assessments in [Appendix 1](#) and [Appendix 2](#). If a patient is at risk for exceeding maximal allowable blood draw limits (per Seattle Children's Hospital Guideline for Maximum Blood Volumes, [Appendix 6](#)), the blood draw schedules for laboratory assessments may be adjusted within the guidelines outlined in [Section 7](#) to ensure patient safety.

Clinical laboratory tests can be measured as part of the screening visit or within 14 days prior to the start of the screening window on a non-screening test if the test was performed as part of patient's routine standard of care. Therefore, if a patient's normal SOC labs include all labs required as screening labs for the protocol and are done within 28 days prior to baseline, these labs can be considered to serve as the patient's protocol-mandated screening labs, and elevated AST/ALT (> 2.5 times the upper ULN) or bilirubin (> 1.5 times the ULN) values therein can be considered as liver risk factors in the inclusion criteria for the study.

During the study, clinically significant changes in routine laboratory tests will be considered AEs ([Section 6.8.1.1](#)).

**Table 7 Clinical Laboratory Tests**

Serum Chemistry	Hematology
Alanine aminotransferase (ALT)	Hemoglobin
Albumin	Hematocrit
Alkaline phosphatase	Mean corpuscular volume (MCV)
Aspartate aminotransferase (AST)	White blood cell count (WBC) with differential
Blood urea nitrogen (BUN)	Platelet count
Calcium	
Chloride	
Creatinine	Coagulation
Creatinine clearance (CrCl) a	Activated partial thromboplastin time (aPTT)
Cystatin C (optional) b	International normalized ratio (INR)
Glomerular filtration rate (GFR; optional) b	
Glucose	
Magnesium	
Phosphorus	
Potassium	

Defibrotide (JZP-381)  
Clinical Trial Protocol: 15-007 Version 4.0

Jazz Pharmaceuticals, Inc.  
20 August 2018

**Table 7 Clinical Laboratory Tests**

Serum Chemistry	Hematology
Sodium	
Total bilirubin, direct bilirubin, and indirect bilirubin	
Total protein	

a Creatinine clearance will be calculated using Cockcroft-Gault formula for adults and Schwartz formula for pediatric patients.

b If cystatin C is measured, GFR will be calculated using either the Grubb or Larsson formula.  
GFR= Glomerular filtration rate

Clinical laboratory parameters listed in the inclusion/exclusion criteria must be reviewed (see [Section 4.1](#) and [Section 4.2](#)). The investigator will provide an explanation of all clinically significant laboratory observations, and these findings will be recorded as AEs.

### 6.8.2.2 Other Laboratory Tests

Screening laboratory tests include a serum or urine pregnancy test for women of child-bearing potential. A serum or urine pregnancy test will also be performed at Day +30 post-HSCT and Day +60 post-HSCT. For women of child-bearing potential who develop VOD and receive defibrotide, a serum or urine pregnancy test will be performed 30 days after the first dose of defibrotide and 30 days after the last dose of defibrotide.

### 6.8.3 Vital Signs

Vital signs will include blood pressure, pulse, respiratory rate, and body temperature. The method for measuring body temperature (e.g., oral, tympanic, rectal, or axillary) is to be recorded. For all patients, vital signs will be recorded during screening, once daily from baseline through Day+30 post-HSCT or hospital discharge, whichever is sooner; twice weekly after early hospital discharge until Day +30 post-HSCT (if applicable); weekly between Days +31 and +60 post-HSCT; and at the Days +100 and +180 post-HSCT visits. For patients who develop VOD during the study and are administered rescue defibrotide, vital signs will be recorded daily from diagnosis of VOD through hospital discharge, twice weekly through resolution of VOD, 30 days after the last dose of rescue defibrotide, and at the Days +100 and +180 post-HSCT visits.

More intensive vital signs monitoring will be conducted on the first day of defibrotide dosing, which occurs on:

- the day before the first day of the conditioning regimen for patients in the DP arm who receive defibrotide prophylaxis and
- on the first day of defibrotide administration for patients in the BSC arm who receive defibrotide treatment for VOD

For this intensive monitoring, vital signs will be recorded at pre- dose, at 15, 30, 60, and 120 minutes ( $\pm 5$  minutes) following start of infusion and at 15 minutes ( $\pm 5$  minutes) following the end of the first and second infusions.

Defibrotide (JZP-381)  
Clinical Trial Protocol: 15-007 Version 4.0

Jazz Pharmaceuticals, Inc.  
20 August 2018

If patients in the DP arm who receive defibrotide prophylaxis receive rescue defibrotide for the treatment of VOD, intensive vital signs monitoring will be conducted only on the first day of defibrotide prophylaxis regardless of when they move into the rescue arm.

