### 1.6.2 Hypersensitivity

Hypersensitivity reactions have occurred in less than 2% of patients treated with defibrotide; 1 case of anaphylactic reaction was reported in a patient who had previously received defibrotide (see Investigator's Brochure [IB] for Defibrotide). Patients should be monitored for hypersensitivity reactions, especially if there is a history of previous exposure to defibrotide. If a severe hypersensitivity reaction occurs, defibrotide should be discontinued and the hypersensitivity treated according to standard of care, and monitored until symptoms resolve. Patients with a known hypersensitivity to defibrotide or its excipients will be excluded from the study.

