#### 5.2.1.2 Defibrotide Rescue Treatment for Patients who Develop VOD

For patients who develop VOD per modified Seattle criteria in either the DP or BSC arms, defibrotide will be administered as treatment for VOD until resolution of VOD or hospital discharge, whichever is sooner, and may continue beyond Day +30 post-HSCT. Patients must be hemodynamically stable and not at risk of bleeding, as defined in the first 3 exclusion criteria (#1, #2, #3) listed in [Section 4.2](#), to receive defibrotide as rescue treatment for VOD. Patients with VOD undergoing rescue treatment with defibrotide will continue to receive individualized standard of care therapy (BSC) based on local institutional guidelines and patient need. Medications that increase risk of bleeding must be stopped 24 hours prior to the start of defibrotide rescue treatment (see [Section 5.7.6](#)).

Defibrotide administration must be stopped if a patient has clinically significant bleeding. Defibrotide may be re-initiated if the bleeding is controlled and is of severity  $\leq$  grade 1.

The daily dose of defibrotide in patients who receive rescue treatment with defibrotide after being randomized to the DP or BSC arm will be based on body weight at baseline (i.e., within 24 hours before conditioning begins for the DP arm, and on the day that conditioning begins for patients in the BSC arm who develop VOD and subsequently receive defibrotide).

Defibrotide (JZP-381)  
Clinical Trial Protocol: 15-007 Version 4.0

Jazz Pharmaceuticals, Inc.  
20 August 2018

---

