**START OF STUDY TREATMENT:**

- Administration of defibrotide 25 mg/kg/day, given as 4 2-hour infusions of 6.25 mg/kg every 6 hours. Each dose (infused over a 2 hour  $\pm$ 15 min infusion period) may be administered within  $\pm$ 1 hour of the scheduled dosing time provided that there is at least a 2-hour window between the end of an infusion and the start of the next infusion (if randomized to DP arm) or administration of BSC medication(s) (if randomized to BSC arm)
- Patients randomized to DP arm only: Vital signs (blood pressure, pulse, respiratory rate, and body temperature), and intensive monitoring of vital signs only during the first 2 infusions of defibrotide prophylaxis, as follows: 15, 30, 60, and 120 minutes ( $\pm$  5minutes) following start of infusion and at 15 minutes ( $\pm$  5minutes) following the end of the first and second infusions

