##### 7.4.1.2 Assessments During Hospitalization

###### DAILY DURING HOSPITALIZATION

The following procedures and assessments are to be performed daily during hospitalization for treatment of VOD, unless otherwise specified:

- Physical examination, including assessments of the skin, head, eyes, ears, nose, throat, neck, thyroid, lungs, heart, abdomen (with palpation of the liver; and with measurement of abdominal girth for pediatric patients only), lymph nodes, extremities, and a general assessment (including edema). Whenever possible, assessment of right upper quadrant pain will be performed.
- Weight
- Vital signs (blood pressure, pulse, respiratory rate, and body temperature), and intensive monitoring of vital signs only during the first 2 infusions of defibrotide treatment, as follows: pre-dose, and 15, 30, 60, and 120 minutes ( $\pm 5$  minutes) following start of infusion and at 15 minutes ( $\pm 5$  minutes) following the end of the first and second infusions
- Clinical laboratory tests (serum chemistry, hematology, and coagulation). Note: bilirubin must be assessed daily during hospitalization; other serum chemistry and hematology tests may be performed a minimum of 3-times weekly and coagulation parameters may be assessed a minimum of once weekly at the discretion of the investigator (see [Section 7](#) for details) to ensure patient safety ([Appendix 6](#)).

Defibrotide (JZP-381)  
Clinical Trial Protocol: 15-007 Version 4.0

Jazz Pharmaceuticals, Inc.  
20 August 2018

- 
- Calculation of CrCl (using Cockcroft-Gault for adults and Schwartz formula for pediatric patients). If cystatin C is measured, GFR will be calculated using either the Grubb or Larsson formula.
  - Hospitalization information (i.e., dates of hospitalization, dates in ICU, dates of readmission) and inpatient resource use
  - Administration of defibrotide 25 mg/kg/day, given as 4 2-hour infusions of 6.25 mg/kg every 6 hours. Each dose (infused over a 2 hour  $\pm$  15 min infusion period) may be administered within  $\pm$  1 hour of the scheduled dosing time provided that there is at least a 2-hour window between the end of an infusion and the start of the next infusion (all patients); and intensive monitoring of vital signs only during the first 2 infusions of defibrotide treatment, as follows: pre-dose, and 15, 30, 60, and 120 minutes ( $\pm$  5 minutes) following start of infusion and at 15 minutes ( $\pm$  5 minutes) following the end of the first and second infusions

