## Defibrotide (JZP-381)

## Clinical Study Protocol: 15-007 Version 4.0

Jazz Pharmaceuticals, Inc.  
20 August 2018

- c. This visit at 30 days after last dose of defibrotide may be omitted if a weekly scheduled visit between Day +100 and +180 post-HSCT occurs within 7 days after this visit would be scheduled. Safety assessments performed at the visit that occurs 30 days after the last dose of defibrotide need not be repeated at the Day +100 post-HSCT visit if these visits occur within 2 weeks of each other.
- d. If the twice weekly visit falls within the window of the Day +30 post-HSCT visit, the Day +30 post-HSCT assessments should be performed at that visit
- e. Complete physical examination, including assessments of the skin, head, eyes, ears, nose, throat, neck, thyroid, lungs, heart, abdomen (with palpation of the liver and with measurement of abdominal girth for pediatric patients only), lymph nodes, extremities, and a general assessment (including edema). Whenever possible, assessment of right upper quadrant pain will be performed.
- f. Vital signs include blood pressure, pulse, respiratory rate, and body temperature. Intensive monitoring of vital signs will be recorded during the first and second infusion of defibrotide on the first day of defibrotide dosing. For this intensive monitoring, vital signs will be recorded at pre-dose, and 15, 30, 60, and 120 minutes ( $\pm 5$  minutes) following start of infusion and at 15 minutes ( $\pm 5$  minutes) following the end of the first and second infusions.
- g. Clinical laboratory tests include serum chemistry (ALT, albumin, alkaline phosphatase, AST, BUN, calcium, chloride, creatinine, glucose, magnesium, phosphorus, potassium, sodium, total bilirubin [direct and indirect], total protein, CrCl [using the Cockcroft-Gault formula for adults and Schwartz formula for pediatric patients]) and if cystatin C is measured, then GFR [using the Grubb or Larsson formula]; hematology (hemoglobin, hematocrit, MCV, WBC count with differential, platelet count); and coagulation (aPTT, INR).

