8.4.3 Vital Signs

Intensive vital signs recorded during the first and second infusion of defibrotide on the first day of defibrotide dosing will be summarized at the nominal visit and time recorded in EDC. The analysis windows for all other visits will follow Table 1 and Table 2 in [Section 8.4.1](#) for the prophylaxis and rescue phases, respectively.

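### Protocol 6.8.3 and 7.4.1.2 give incompatible instructions on intensive vital signs when a prophylaxis-arm patient starts rescue defibrotide

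*Protocol*

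**What the plan says.** Protocol 6.8.3 places intensive vital signs on the day a patient first receives defibrotide and defines that day by arm. For the DP arm it is the day before conditioning starts. For the best supportive care (BSC) arm it is "on the first day of defibrotide administration for patients in the BSC arm who receive defibrotide treatment for VOD". The section then addresses DP-arm patients who later need rescue: "intensive vital signs monitoring will be conducted only on the first day of defibrotide prophylaxis regardless of when they move into the rescue arm".

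Protocol 7.4.1.2 lists the daily assessments during hospitalization for treatment of veno-occlusive disease (VOD). Both its vital signs bullet and its defibrotide administration bullet call for "intensive monitoring of vital signs only during the first 2 infusions of defibrotide treatment". Neither bullet limits the monitoring by arm. Rescue itself is open to both arms under 5.2.1.2: "For patients who develop VOD per modified Seattle criteria in either the DP or BSC arms, defibrotide will be administered as treatment for VOD".

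Two further texts touch the point. Appendix 2 footnote f, in the schedule for rescued patients, reads "Intensive monitoring of vital signs will be recorded during the first and second infusion of defibrotide on the first day of defibrotide dosing". SAP 8.4.3 uses the same phrase: "Intensive vital signs recorded during the first and second infusion of defibrotide on the first day of defibrotide dosing will be summarized", by nominal visit and time.

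Protocol 1.6.2 is relevant background: "Patients should be monitored for hypersensitivity reactions, especially if there is a history of previous exposure to defibrotide".

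**The concern.** The two protocol sections point in opposite directions for one identifiable group: DP-arm patients at the start of rescue. A site working from 6.8.3 takes no intensive readings at that moment. A site working from the rescue schedule in 7.4.1.2 takes the full set.

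Peri-infusional vital signs in patients who receive defibrotide are part of a stated safety objective (Protocol 2.2), and SAP 11.4 summarizes extreme blood pressure changes to look for hypotension around the infusion. If collection at rescue start depends on which section a site happened to read, the rescue-phase data for DP-arm patients will be uneven between sites. Missing readings could then reflect the document consulted and nothing about the patient.

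**Working it through.** No figure in the plan rests on this point, so the check is a comparison of texts, followed by simple arithmetic for scale.

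**Step 1: can 7.4.1.2 be read as meaning the prophylaxis infusions?** No. Where the protocol means those, in 7.2.1.1, it says "intensive monitoring of vital signs only during the first 2 infusions of defibrotide prophylaxis" and restricts the instruction to the DP arm. Section 7.4.1.2 speaks of treatment, sits under the VOD treatment period and has no such restriction.

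**Step 2: the instructions side by side, for a DP-arm patient starting rescue.**

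| Text | Intensive readings at rescue start? |
|---|---|
| Protocol 6.8.3, list by arm | Provided for the BSC arm only |
| Protocol 6.8.3, last paragraph | No, whenever rescue begins |
| Protocol 7.4.1.2, vital signs bullet | Yes, first 2 rescue infusions |
| Protocol 7.4.1.2, administration bullet | Yes, first 2 rescue infusions |
| Protocol Appendix 2, footnote f | Ambiguous |
| SAP 8.4.3 | Ambiguous |

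The last two rows are ambiguous because they refer to the first day of dosing. Taken as 6.8.3 defines that day, they agree with 6.8.3. Taken in the setting of a rescue schedule, footnote f would more naturally mean the first rescue day. Neither text says which applies to a patient who has already had prophylaxis.

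**Step 3: readings per patient.** The time points in 7.4.1.2 are pre-dose; 15, 30, 60 and 120 minutes from the start; and 15 minutes after the end. That is 6 per infusion, and 6 x 2 infusions = 12 (11 if a single pre-dose reading is taken). Under 6.8.3 the number at rescue start is 0.

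**Step 4: how many patients, for scale only.** The plan does not give the number of DP-arm rescues. Two figures in the documents indicate the order of size:
- Design rate of VOD or death by Day +30 in the DP arm (Protocol 9.3): 0.14 x 200 = 28 patients.
- VOD rate on defibrotide in the earlier randomized pediatric prevention trial (Protocol 1.2): 22/180 = 12.2%, and 0.122 x 200 is about 24 patients.

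**The case against.** The best defense is that 6.8.3 is a deliberate, arm-specific exception and that a specific rule overrides a general one. These patients already had intensive readings at their first prophylaxis infusions, and rescue uses the same dose and regimen, so a patient still on prophylaxis at diagnosis may simply continue. This is a possible intention. However, neither 7.4.1.2 nor Appendix 2 refers to the exception, so a site using the rescue schedule would not find it.

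Several points for the defense stand and limit the finding:

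- **Footnote f.** A reader might count Appendix 2 footnote f as a third contradiction. With the by-arm definition in 6.8.3 it can be read consistently with that section, so it is ambiguous and no more.
- **The administration bullet.** Its parenthesis extending to every patient closes the dosing clause, before the monitoring clause begins. It says who is dosed. The argument rests on the absence of any arm restriction on the monitoring.
- **Previous exposure.** A reader might infer that 6.8.3 contradicts 1.6.2, or that patients singled out for extra watching would get no monitoring. Section 1.6.2 asks for monitoring for hypersensitivity but sets no vital sign schedule. Daily vital signs, daily examination and adverse event monitoring continue during inpatient rescue under either section.
- **Re-exposure.** It would go too far to say that the trial could not assess the safety of re-exposure. Hypersensitivity reactions are summarized as events of special interest (SAP 11.2.1), with safety reported by arm and phase (SAP 11).

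**Conclusion.** The conflict between Protocol 6.8.3 and 7.4.1.2 is real: for a DP-arm patient starting rescue, both cannot be followed. The difference is 12 intensive readings or none at rescue start, on top of routine monitoring that is unchanged. The consequence is inconsistent collection of rescue-phase peri-infusional vital signs in the DP arm.

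The figures of 28 and 24 patients only show scale. It would be tempting to treat 28 as an upper limit, since the 14% includes deaths. The documents do not support that: rescue follows the investigator's diagnosis, the adjudication committee may not confirm it (SAP 10.1 provides for this in the BSC arm), and rescue can begin after Day +30. Nor do these figures count patients restarting after a break, a number the plan does not give.

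This is a lower-grade internal inconsistency in safety monitoring. It has no effect on the primary or key secondary analysis. No view is taken here on which instruction is clinically right.

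**What to change.** 1. Reconcile Protocol 6.8.3 (the list by arm and the last paragraph) with both bullets of 7.4.1.2, so that they give one instruction on intensive vital signs for DP-arm patients starting rescue. The choice is a clinical decision for the sponsor, who should consider 1.6.2 on previous exposure when making it.
2. Align Appendix 2 footnote f and SAP 8.4.3 with that instruction, stating which first day is meant for a patient who has already received prophylaxis.

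The cost is one protocol clarification and a wording change in the SAP. No new SAP table is needed: by default, safety summaries are already presented by study phase and by treatment received during the Prophylaxis Phase (SAP 8.3), which separates rescued patients from the two arms.
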